### 9.8.3.6 **Development of Veno-Occlusive Disease after Day +30 and By Day +180 Post-Hematopoietic Stem Cell Transplant**

The incidence of VOD after Day +30 post-HSCT will also be summarized and compared between the 2 treatment arms using a chi-square test as appropriate.

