4.5 Randomization Procedures and Blinding

After informed consent or assent has been obtained from subjects, or legal parent/guardians or representatives, as applicable, screening procedures will be performed within 14 days of the scheduled start of the subject's HSCT conditioning regimen. Eligible subjects will be randomly assigned to receive DP 25 mg/kg/day in addition to BSC (DP arm) or BSC alone (BSC arm) in a 1:1 ratio. Randomization will be stratified according to risk of developing VOD (high-risk or very high-risk), age (>16 years or ≤16 years), and country using an interactive web response system (IWRS). Enrollment of those subjects meeting high-risk criteria will be capped at 65% of the total enrollment using IWRS.

This is an open-label study. To minimize potential for bias, the following blinding measures will be employed:

- The central reviewer of imaging studies will be blinded to study treatment assignment and all non-radiologic subject data (see protocol Section 6.3.1.2).
- Members of the EPAC will be blinded to study treatment assignment, will not be employees of the Sponsor, and will not be otherwise involved in the study (see protocol Section 6.3.1.3 and Section 11.9.2).

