10 EFFICACY

Although randomization is stratified by 3 variables, only 2 stratification variables (very high risk or high risk and pediatric [≤ 16 years] or adults [> 16 years]) recorded in IRT will be used in the stratified tests described in this section (ie, the stratified log-rank test, the stratified Cox proportional hazards regression model and Cochran-Mantel-Haenszel [CMH] test) for the primary efficacy endpoint and the secondary efficacy endpoints, as appropriate. These 2 stratification variables yield 4 distinct strata corresponding to unique levels of randomization strata. If there are fewer than 20 subjects in at least 1 of the 4 distinct strata, only the very high risk/high risk strata will be used in the stratified tests. Although the randomization will be stratified by country as well to ensure balance of treatment, due to the expected low enrollment within some countries, the stratified efficacy analyses will not be stratified by country.

Analyses and summaries using the ITT and mITT analysis sets will be stratified using data reported in the IRT system at the time of randomization. If the number of subjects with discrepancies between IRT and EDC with regard to stratum assignment is greater than or equal to 5% of the randomized subjects, the primary and key secondary efficacy endpoint analyses will be repeated using the stratum assignment reported in EDC as sensitivity analyses.

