10.2.2 Other Secondary Efficacy Endpoints

These other secondary efficacy endpoints will be tested without multiplicity adjustments, and nominal p-values will be reported. The ITT Analysis Set will be used for these analyses.

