10.2.2.1 Incidence of VOD by Day +30 post-HSCT

The incidence of EPAC-assessed VOD by Day +30 post-HSCT will be compared between treatment arms using the CMH test stratified by 2 stratification variables for randomization (very high risk/high risk and pediatric/adults).

The following summary will be provided:

- Incidence of VOD by Day +30 post-HSCT

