10.2.2.4 Incidence of VOD-associated MOD by Days +30 and +100 post-HSCT

VOD-associated MOD is defined for subjects as occurring if the investigator answers “Yes” to the question “Has the subject been diagnosed with VOD associated MOD?” in the eCRF. The number and proportion of subjects who develop VOD-associated MOD by Days +30 and +100 post-HSCT will be summarized and compared between the 2 treatment arms using a chi-square test.

The following summary will be provided:

- Summary of VOD-associated MOD

The following listing will be provided and will include the date of MOD and type of renal and pulmonary dysfunction:

- Listing of VOD-associated MOD

10.2.2.5 Resolution of VOD by Day +180 post-HSCT and Time to Resolution of VOD

Of those subjects who were diagnosed with VOD by Day +30 post-HSCT by the investigator, the proportion of subjects who have resolution of VOD by Day +180 post-HSCT will be summarized by treatment arm.

Time to resolution of VOD will be calculated as follows:

Time to resolution of VOD = [Date of VOD resolution] – [Date of VOD diagnosis by investigator]

If VOD does not resolve by Day +180 post-HSCT, the subject will be censored on the date of the Day +180 post-HSCT VOD resolution assessment. If the Day +180 post-HSCT VOD resolution assessment is missing, they will be censored on the date of the last VOD resolution assessment performed.

The following will be presented for VOD resolution by Day +180 post-HSCT:

- The number of subjects by treatment group who had an event and who were censored (either due to not having an event or for other reasons as described above).
- The p-value from a log rank test stratified by risk status and age group.
- The KM estimates of the NRM rate (%) with 95% CI.
- the KM estimate of median time to NRM in days (95% CI).
- The HR (95% CI) from a Cox proportional hazards regression model stratified by risk status and age group.
- A KM plot will be presented up to Day +180 post-HSCT for each treatment arm. The number of subjects at risk will be displayed at 10-day intervals.

The following summary will be provided:

- Analysis of VOD resolution by Day +180 post-HSCT

The following figure will be provided:

- Figure of VOD resolution by Day +180 post-HSCT

The following listing will be provided and will include whether or not VOD was resolved, the criteria met for resolution, and the date of resolution:

- Listing of VOD resolution

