10.2.2.6 Incidence of VOD by Day +100 post-HSCT and Day +180 post-HSCT

The number and proportion of subjects who develop VOD after Day +30 post-HSCT but by Day +100 post-HSCT and by Day +180 post-HSCT will be summarized and compared between the treatment arms using a chi-square test at each timepoint. The diagnosis of VOD through Day +100 post-HSCT will be made by EPAC, and the diagnosis of VOD after Day +100 post-HSCT will be based on investigator assessments.

The following summary will be provided:

- Incidence of VOD by Day +100 post-HSCT and Day +180 post-HSCT in subjects who develop VOD after Day +30

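### MOD and late VOD are compared with an unstratified chi-square test although randomisation is stratified by risk and age: a small, avoidable power loss for MOD, and a consistency point only for late VOD

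*SAP*

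**What the plan says.** - **MOD.** SAP 10.2.2.4: the proportions with VOD-associated MOD by Days +30 and +100 "will be summarized and compared between the 2 treatment arms using a chi-square test". Protocol 9.8.3.4 also names a chi-square test.
- **Late VOD.** SAP 10.2.2.6: VOD arising after Day +30, counted by Day +100 and by Day +180, "will be summarized and compared between the treatment arms using a chi-square test at each timepoint". Protocol 9.8.3.6 has the comparison made "using a chi-square test as appropriate".
- **Randomisation and strata.** SAP 4.5 stratifies randomisation by risk, age and country. SAP 10 uses risk and age in the stratified tests, CMH among them, "for the primary efficacy endpoint and the secondary efficacy endpoints, as appropriate". It falls back to risk alone if any of the four cells has fewer than 20 subjects. Neither document says why strata would be inappropriate for MOD or late VOD.
- **Neighbouring endpoints.** VOD by Day +30 is compared "using the CMH test stratified by 2 stratification variables for randomization" (SAP 10.2.2.1), and the binary composite in SAP 10.1.1.2 is handled the same way. Non-relapse mortality and time to VOD resolution get stratified log-rank tests (SAP 10.2.2.3 and 10.2.2.5).
- **Status and denominator.** Under SAP 10.2.2 these endpoints "will be tested without multiplicity adjustments, and nominal p-values will be reported", using the ITT set. The endpoint list in SAP 4.3.2.3, however, confines MOD incidence to subjects who develop VOD.

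**The concern.** Risk group was chosen because it predicts VOD. Protocol 1.5 puts VOD at 20-25% in high-risk and 30-60% in very high-risk patients. Stratified 1:1 randomisation balances risk between the arms, so differences in rate between strata add almost nothing to the true variance of the treatment difference. A pooled chi-square test still counts that between-stratum variation as noise. Its standard error is then too large, its type I error falls below nominal, and some power is lost. MOD is the endpoint closest to severe disease, and the stratified test is already specified for VOD by Day +30.

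**Working it through.** **The plan's own figures.** No power or sample size is stated for MOD or late VOD. The primary design, which supplies the sample size, does reproduce. HR = ln(0.86)/ln(0.72) = 0.459. With 68 events, power = Φ(|ln 0.46| × √68/2 − 1.96) = Φ(3.202 − 1.960) = 0.893, against a stated 90%.

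**Inputs.** 200 per arm (SAP 4.6), 1:1 allocation (SAP 4.1) and a 65/35 risk split (protocol 1.5), so 130 + 70 patients per arm. Denominator: ITT (SAP 10.2.2). Control rates by stratum are assumptions.

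**Formula.** With stratum shares w, rates p and overall rate p̄, the true variance of the difference is R times what the pooled test assumes:

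R = Σ w·p·(1−p) / [p̄(1−p̄)]

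True two-sided type I error = 2 × P(Z > 1.96/√R). Where the stratified test has power P, the unstratified test has Φ(z_P + 1.96 − 1.96/√R).

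**Worked example, 5%/20%.** p̄ = 0.65×0.05 + 0.35×0.20 = 0.1025. Denominator: 0.1025×0.8975 = 0.0920. Numerator: 0.65×0.0475 + 0.35×0.16 = 0.0869. R = 0.944 and 1.96/√R = 2.017. Type I error = 0.044, and 80% power becomes Φ(0.842 + 1.960 − 2.017) = 78.4%.

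**Worked example, 5%/30%.** p̄ = 0.1375; R = 0.1044/0.1186 = 0.880; 1.96/√R = 2.089. Type I error = 0.037.

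**Simulation.** At least 200,000 trials per setting, 400 patients, arms equal within risk stratum, no continuity correction, CMH stratified by risk only. The treatment effect halves either the risk (RR 0.5) or the odds (OR 0.5).

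| Control rates, high/very high | R | Type I, chi-square | Type I, CMH | Power, chi-square | Power, CMH | Effect |
|---|---|---|---|---|---|---|
| 1%/3% | 0.995 | 0.045 | 0.045 | 10.4% | 10.4% | RR 0.5 |
| 2%/5% | 0.993 | 0.047 | 0.047 | 15.9% | 15.9% | RR 0.5 |
| 5%/10% | 0.991 | 0.046 | 0.048 | 33.0% | 33.3% | RR 0.5 |
| 5%/15% | 0.971 | 0.044 | 0.050 | 35.9% | 37.5% | OR 0.5 |
| 5%/20% | 0.944 | 0.042 | 0.049 | 40.5% | 43.1% | OR 0.5 |
| 10%/30% | 0.936 | 0.044 | 0.050 | 59.4% | 61.5% | OR 0.5 |
| 5%/30% | 0.880 | 0.037 | 0.049 | 47.5% | 52.0% | OR 0.5 |

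In the first three rows R is almost 1, so most of the shortfall from 0.05 comes from sparse counts and CMH largely shares it.

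**Late VOD.** Protocol 1.4 places VOD typically within the first 21 days and calls later cases infrequent. No rate is given. The first two rows are the plausible range, and there the two tests behave alike. At the 600-patient maximum with 2%/5%, chi-square is 0.2 points ahead (23.8% against 23.6%).

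**The case against.** **The choice is deliberate and agrees across documents.** The protocol names chi-square for both endpoints, and SAP 10 requires strata only where appropriate. So a reader should not infer a drafting slip in the SAP, or that every other binary efficacy endpoint uses CMH: the proportion with VOD resolution is binary and is only summarised. This stands. It still leaves MOD and late VOD as the only binary efficacy comparisons tested without strata, and no reason is given. The SAP has already added strata to time to resolution, where protocol 9.8.3.5 names only a log-rank test.

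**The larger figures need a contrast that the documents do not supply.** This also stands. Protocol 1.2 reports severe VOD in 3 of 7 VOD cases (43%) among osteopetrosis controls. Applying that share to 20% and 60% VOD gives 8.6%/25.7%, for which R = 0.946, type I error is 0.044 and 80% power becomes 78.4%. That is a loss of 1.6 points, at the widest stratum contrast in protocol 1.5. The series is tiny, and the calculation assumes the same severe share in both strata. In favour of a wider contrast there is only the raw 3 of 11 (27%) from the same series. At an assumed 5%/27%, type I error is 0.039 and 80% becomes 76.9%.

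**The MOD denominator is unsettled.** If MOD is compared only among patients with VOD, the groups are a post-randomisation subset with no guaranteed balance by stratum, and the variance argument no longer applies. This stands and limits the point to ITT.

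**Sparse data matter more for late VOD.** At 1%/3%, 400 × 0.017 = 6.8 events are expected, or 3.4 per arm. Neither large-sample test is comfortable there, and the collapse rule in SAP 10 counts subjects, not events. This stands, and CMH does not cure it.

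**Conclusion.** The point holds as a minor one. On the ITT set the unstratified test is valid but mildly conservative for MOD, and how much depends on stratum rates that the documents do not give. A loss of up to about 2.5 points covers the moderate contrasts examined; 4.5 points needs a sixfold difference between strata. For late VOD there is no demonstrable gain, and the argument is consistency of method.

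Two stronger readings are tempting and unsupported. One is that both endpoints lose several points of power: this carries an assumed MOD contrast over to an endpoint described as infrequent, and protocol 1.5 and its Table 3 do not show that late VOD differs by risk. The other is that the trial's conclusions are at stake: these p-values are nominal and outside the testing hierarchy, and the error is in the conservative direction.

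The figures assume 200 per arm, a 65/35 split, arms balanced within risk stratum, stratification by risk only, and the ITT denominator.

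**What to change.** 1. In SAP 10.2.2.4 (MOD, Days +30 and +100) and 10.2.2.6 (late VOD, Days +100 and +180), replace the chi-square test with the CMH test of 10.2.2.1, using the same strata and the SAP 10 collapse rule, and state the ITT denominator for both.
2. Record the departure from protocol 9.8.3.4 and 9.8.3.6 in SAP Section 5.
3. Reconcile the MOD denominator between SAP 10.2.2 and 4.3.2.3. If a summary among VOD patients is kept, present it as descriptive.
4. Optionally, name an exact stratified test for use when events are few.

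The cost is two SAP sentences, a Section 5 entry and one denominator clarification. The CMH analysis is already planned for VOD by Day +30, so no new data or strata are needed. Done before the database freeze that SAP Section 3 sets as the limit for analysis decisions, the change remains prespecified. If the team prefers chi-square, one sentence giving the reason would also close the point.

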10.2.2.6 Incidence of VOD by Day +100 post-HSCT and Day +180 post-HSCT

The number and proportion of subjects who develop VOD after Day +30 post-HSCT but by Day +100 post-HSCT and by Day +180 post-HSCT will be summarized and compared between the treatment arms using a chi-square test at each timepoint. The diagnosis of VOD through Day +100 post-HSCT will be made by EPAC, and the diagnosis of VOD after Day +100 post-HSCT will be based on investigator assessments.

The following summary will be provided:

- Incidence of VOD by Day +100 post-HSCT and Day +180 post-HSCT in subjects who develop VOD after Day +30

11 SAFETY

Safety summaries will be provided by treatment arm and study phase based on the Safety Analysis Set.

11.1 Extent of Exposure

Defibrotide administration will be summarized for the Prophylaxis and Rescue Treatment phases. The following will be summarized and listed:

- Days of study drug treatment: The number of days the subject received at least one dose of study drug treatment.
- Duration of study drug treatment in days: (date of last dose – date of first dose) +1
- The total number of doses received
- The number of doses per day: Total number of doses received divided by the duration of study drug treatment.
- Total exposure (mg): Total amount of study drug received by the subject in mg.
- The daily dose in mg/day: Total exposure divided by the duration of treatment.
- The daily dose in mg/kg/day: Total exposure divided by the duration of study drug treatment in days, and then divided by Baseline weight in kg.

The following summary will be provided:

- Summary of defibrotide administration

The following listing will be provided:

- Listing of defibrotide administration
- List of subjects receiving test drug from specific batches

11.2 Adverse Events

Adverse events recorded in the case report form will be coded to SOC and PT using the MedDRA 19.1. The investigator will assess the relatedness of each AE to study drug. The severity of AEs will be recorded using the Common Terminology Criteria for Adverse Events (CTCAE 4.03).

At a minimum, for subjects in either the DP or BSC arm, the investigator must record all AEs and SAEs that occur from the time written informed consent is obtained until screen failure if applicable, or Day +60 post-HSCT, regardless of their relationship to study drug or procedure. Even if the minimum of Day +60 post-HSCT is met, the investigator must continue to record all AEs and SAEs that occur within 30 days after the last dose of defibrotide, regardless of their relationship to study drug or procedure. For subjects who do not receive HSCT, AEs must be collected for 70 days after Baseline or early termination, whichever occurs first. For subjects randomized but not treated, AEs will be collected for 70 days after randomization or early termination, whichever is earlier. Any SAE assessed as related to defibrotide or study procedures by the investigator should be reported regardless of time after study termination. Related SAEs reported after study termination will be collected in the Safety database only.

A treatment-emergent adverse event (TEAE) is defined as any event with onset date on or after the first dose of study treatment (either DP or conditioning regimen) or any ongoing event that worsens in severity after the date of the first dose of study treatment through the protocol-specific reporting period. Only TEAEs with the onset date on or before the end of the protocol-specific AE reporting period noted above will be included in summary tables unless otherwise specified. All AEs will be listed. For the purpose of calculating treatment emergence, incomplete onset dates will be imputed as detailed in Section [8.1.2.1](#).

AEs are graded by the investigator as Grade 1 (mild), Grade 2 (moderate), Grade 3 (severe), Grade 4 (life threatening), or Grade 5 (fatal). The severity grade of events for which the investigator did not record severity will be categorized as “missing” for tabular summaries and data listings, and will be considered the least severe for the purposes of sorting for data presentation.

Treatment-related AEs are those for which the investigator answers “Yes” to the question “Was this adverse event related to study treatment?” in the eCRF. Events for which the investigator did not record relationship to study treatment will be considered related to study treatment in summaries if the subject received defibrotide. They will be considered not related if the subject did not receive defibrotide. Data listings will show treatment relationship as missing.

Serious AEs are those for which the investigator answers “Yes” to the question “Was the adverse event serious?” in the eCRF. The clinical database will be reconciled with the serious AE database before database finalization.

For all AE summaries, if a subject has more than 1 AE within a PT, the subject is counted only once at the maximum severity and with the closest relationship to study drug. If a subject has more than 1 AE within a SOC, the subject is similarly counted once when reporting results for that SOC. SOC and PT will be sorted by frequency in the DP arm and then alphabetically for those with the same frequency.

The following summaries will be provided (all summaries except the overall summary will be presented by SOC and PT within SOC):

- Overall summary of TEAE

- Summary of TEAE by SOC and PT
- Summary of TEAE by PT
- Summary of TEAE by age group
- Summary of serious TEAE
- Summary of treatment-related TEAE
- Summary of serious treatment-related TEAE
- Summary of Grade 3 or 4 TEAE
- Summary of treatment-related Grade 3 or 4 TEAE
- Summary of TEAE leading to study drug discontinuation
- Summary of treatment-related TEAE leading to study drug discontinuation
- Summary of TEAE by maximum toxicity grade
- Summary of treatment-related TEAE by maximum toxicity grade
- Summary of TEAE leading to death
- Summary of treatment-related TEAE leading to death
- Summary of TEAE by SOC and PT including events recorded outside of the protocol-specific AE reporting period
 - Some sites continued to record AEs beyond the protocol-defined reporting period. This table will summarize all AEs with onset date on or after the first dose of study treatment (either DP or conditioning regimen) through the end of the study.

Additionally, the following TEAE summaries for public disclosure will be provided:

- Summary of treatment-emergent serious AEs (for public disclosure)
- Summary of treatment-emergent non-serious AEs occurring in greater than 5% of subjects (for public disclosure)

The following listings will be provided along with subject number, treatment arm, verbatim term, SOC, PT, start date, end date, treatment-emergent flag, severity grade, seriousness, relationship to defibrotide, relationship to a study procedure, action taken, and outcome of the AE:

- Listing of all AEs
- Listing of SAEs
- Listing of Grade 3 and 4 AEs
- Listing of AEs leading to study drug discontinuation
- Listing of AEs leading to death

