#### **6.8.1.5 Adverse Event Recording and Reporting**

At a minimum, for patients in either the DP or BSC arm, the investigator must record all AEs and SAEs that occur from the time written informed consent is obtained until Day +60 post-HSCT (or screen failure), regardless of their relationship to study drug or procedure.

Even if the minimum of Day +60 post-HSCT is met, the investigator must continue to record all AEs and SAEs that occur within 30 days after the last dose of defibrotide, regardless of their relationship to study drug or procedure.

For patients who do not receive HSCT, AEs must be collected for 70 days after baseline or early termination, whichever occurs first. For patients randomized but not treated, AEs will be collected for 70 days after randomization or early termination, whichever occurs first.

Any SAE assessed as related to defibrotide or study procedures by the investigator, regardless of time after study termination, must also be recorded.

SAEs must be reported to the Sponsor or its designee using the SAE Reporting Form within 24 hours of first knowledge of the event by study site personnel. Serious adverse event Reporting Forms and contact information will be provided to the study sites separately.

The SAE Reporting Form must be completed as thoroughly as possible before transmittal to the contact provided on the form. The investigator must provide his/her assessment of causality to the study drug and the study procedure at the time of the initial report. If the investigator does not provide a causality assessment of the SAE at the time of the initial report, the event by default will be presumed to be “related”. Follow-up SAE information must be provided to the Sponsor if there are any updates to SAE information previously provided.

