Administration of defibrotide to subjects in the DP arm will begin within 24 hours of the first dose of conditioning regimen, and will continue (for those subjects without a VOD diagnosis) for a recommended minimum of 21 days and end no later than Day +30 post-HSCT. For subjects in the BSC arm, administration of BSC according to institutional guidelines and subject need will begin on the first day of conditioning and continue until Day +30 post-HSCT or hospital discharge, whichever is sooner, or diagnosis of VOD, if applicable.

If subjects in either the DP or BSC arm develop VOD, per the modified Seattle criteria, they may receive rescue defibrotide treatment for VOD as prespecified in the informed consent and/or assent forms. For subjects in either arm who develop VOD, defibrotide for treatment of VOD should be administered until resolution of VOD or hospital discharge.

Subjects will continue to be monitored for development of late-onset VOD through Day +180 post-HSCT. Subjects who develop clinical signs and symptoms of VOD after hospital discharge/Day +30 post-HSCT will require more frequent monitoring (refer to specific instructions within schedule of assessments in the protocol), and re-admission to the hospital will be at the investigator's discretion.

An independent Endpoint Adjudication Committee (EPAC) blinded to study treatment assignment will be established to determine whether a subject meets the criteria for VOD by Day +30 post-HSCT and by Day +100 post-HSCT, using the modified Seattle criteria. The EPAC will review relevant electronic case report forms (eCRFs), results of diagnostic procedures, and ultrasound results; alternate etiology (eg, cholecystitis, viral hepatitis, acute graft-versus-host disease [GvHD]) will also be considered during review of subject data.

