8 DATA HANDLING CONVENTIONS

8.1 Missing Data

8.1.1 Imputation of Non-Date Missing Data

Missing data occurs when any requested data is not provided, leading to blank fields on the collection instrument. These data will be indicated by the use of a "blank" in subject listing displays. Note that if any missing data is imputed, the imputed data will only be used in

summaries, and will not be included in any listing. Answers such as “Not applicable” and “Not evaluable” are not considered to be missing data and should not be displayed as missing.

Subjects with the designation of treatment relationship for AEs and SAEs missing will have the worst case assumed to impute the relationship: if relationship to study treatment is missing it will be assumed to be “Yes”. There will be no other imputation for missing data other than as described in Section [8.1.2](#) for partial dates and times.

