8.3 Study Phase

In this study, the occurrence of VOD and the administration of rescue defibrotide represent a clinical landmark time point for safety. Therefore, for the safety analyses, 2 study phases are defined with respect to the administration of rescue defibrotide, as follows:

- **Prophylaxis Phase:**
 - If VOD occurs, the prophylaxis phase starts on the Baseline date and ends on the day before the start date of rescue defibrotide (ie, rescue treatment start date – 1).
 - If VOD does not occur, the prophylaxis phase starts on the Baseline date and ends on the date of study completion/early termination.
- **Rescue Treatment Phase:**
 - For the subset of subjects who developed VOD and received rescue defibrotide, the rescue treatment phase begins on the start date of rescue defibrotide and ends on the date of study completion/early termination.

The start date of rescue defibrotide will be derived as the date of the first administration of defibrotide on or after the investigator diagnosis of VOD.

Unless otherwise noted, safety summaries will be reported by study phase and by treatment received during the Prophylaxis Phase.

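### SAP 8.1.1 and 11.2 give opposite rules for a missing adverse-event relationship in BSC subjects never given defibrotide, and neither rule considers event timing

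*SAP*

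**What the plan says.** SAP 8.1.1 (Imputation of Non-Date Missing Data) sets a general rule: "Subjects with the designation of treatment relationship for AEs and SAEs missing will have the worst case assumed to impute the relationship". It then states that "if relationship to study treatment is missing it will be assumed to be" Yes, with no condition on arm or exposure, and closes with "There will be no other imputation for missing data other than as described in Section" 8.1.2, which covers partial dates and times.

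SAP 11.2 (Adverse Events) sets a conditional rule. An event with no recorded relationship "will be considered related to study treatment in summaries if the subject received defibrotide". For everyone else, "They will be considered not related if the subject did not receive defibrotide".

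Three other places bear on this:

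- SAP 4.1 says of subjects in either arm who develop VOD that "they may receive rescue defibrotide treatment for VOD as prespecified" in the consent or assent forms. A BSC subject can therefore become exposed to defibrotide part-way through.
- SAP 8.3 says that, when VOD occurs, the Prophylaxis Phase "ends on the day before the start date of rescue defibrotide". Safety summaries are presented by phase and by the treatment received in that phase.
- Protocol 6.8.1.5 says that, if an initial SAE report has no causality assessment, "the event by default will be presumed to be" related, again with no exposure condition.

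**The concern.** The SAP is meant to let two programmers reach the same table independently. Here each could follow one section faithfully and produce different BSC columns in the treatment-related summaries. Comparing the safety of defibrotide plus BSC with BSC alone is a stated secondary objective, and these tables present part of that comparison.

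The unconditional rule also produces an odd result: it can label events as treatment-related in subjects who never had the drug. The 11.2 rule appears designed to prevent this, but it tests whether the subject was ever exposed, not whether exposure came before the event. For a rescued BSC subject, a later treatment decision then settles how an earlier event is classified.

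**Working it through.** No figure in the plan needs reproducing. The check sets the two rules side by side for each kind of subject and event, given a missing relationship.

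**Do the rules cover the same output?** Yes. SAP 8.1.1 says imputed values are used in summaries and kept out of listings. SAP 11.2 applies its rule in summaries and shows the relationship as missing in listings. The conflict cannot be explained as one rule for tables and another for listings.

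**Which subjects are in scope?** The Safety Analysis Set (SAP 6.4) takes DP-arm subjects with at least one defibrotide dose and all subjects randomized to BSC. TEAEs (SAP 11.2) start from the first DP dose or conditioning, so a BSC subject's events before rescue count as TEAEs.

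| Case (relationship missing) | SAP 8.1.1 | SAP 11.2, literal reading | Result |
|---|---|---|---|
| DP subject, dosed | related | related | agree |
| BSC subject, never given defibrotide | related | not related | contradiction |
| BSC subject, rescued, event after rescue start | related | related | agree |
| BSC subject, rescued, event before rescue start | related | related | agree, but no defibrotide had yet been given |
| DP-arm subject, never dosed | – | – | outside the Safety Analysis Set |

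The second row is the contradiction. The fourth row is a different problem and is shared by both rules. For example, take a BSC subject with an event on Day +3 and rescue starting on Day +18. The event falls in the Prophylaxis Phase, which ends on Day +17. Section 8.1.1 makes it related unconditionally. Section 11.2 makes it related because the subject did, at some point, receive defibrotide.

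**Which tables are exposed?** SAP 11.2 lists six treatment-related TEAE summaries: all, serious, Grade 3 or 4, leading to study drug discontinuation, by maximum toxicity grade, and leading to death.

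**How many subjects fall in each BSC row?** This is an illustration only. The planned arm size is 200 (SAP 4.6). Assume a rescued fraction between 20% (control-group VOD by Day +30 in the earlier paediatric prevention trial, Protocol 1.2) and 28% (the design assumption for VOD or death in BSC, SAP 4.6, which includes deaths and so is not a rescue rate).

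- Rescued: 200 × 0.20 = 40 to 200 × 0.28 = 56.
- Never rescued: 200 − 56 = 144 to 200 − 40 = 160.

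These are subjects to whom a row could apply, not subjects affected. A subject is affected only if an event has a missing relationship, and the documents give no rate for that.

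**The case against.** **The specific section governs the general one.** This is a natural convention, and 11.2 is the more specific text. But the SAP states no precedence, 8.1.1 expressly excludes other non-date imputation, and SAP Section 5 does not list the point as a change. The conflict stands.

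**The timing problem is only one reading.** Section 11.2 gives no time frame. Because safety tables are built by phase, a programmer could apply the exposure test within phase and classify a pre-rescue BSC event as not related. That is fair: the text is silent on timing, and the result above follows from its literal wording. A reader might also infer that back-dating is a defect of 11.2 alone. It is not, since 8.1.1 gives the same answer for those events.

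**Missing relationships may be rare.** Protocol 6.8.1.4 requires the investigator's assessment, and SAP 11.2 plans reconciliation with the serious AE database. This limits the likely size but does not resolve which rule applies.

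**A percentage could be attached.** If 0.5% to 1% of events lacked a relationship and each subject had 8 to 15 events, 1 − (1 − m)^k gives 1 − 0.995^8 = 3.9% to 1 − 0.99^15 = 14.0% of never-exposed BSC subjects with an imputed related event under 8.1.1. The documents support neither input, and the formula assumes independent missingness, although gaps may cluster by site or subject. Nor would the figure under 11.2 be zero overall: only the imputed part is zero, because an investigator may still have recorded Yes. The range should not be used as an estimate.

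**Not all six tables move equally.** This is correct. A never-rescued BSC subject has no defibrotide to stop, so the discontinuation table should barely change. All-causality and special-interest summaries do not use relatedness, and no between-arm test of relatedness is planned.

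**Study treatment includes BSC.** Protocol 4.1 defines it so, and the eCRF question refers to study treatment. A related event in an unexposed BSC subject is therefore not impossible in principle. However, 11.2 also describes investigator relatedness as relatedness to study drug, and its imputation rule turns on defibrotide.

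**Conclusion.** The contradiction between SAP 8.1.1 and 11.2 is explicit for BSC subjects never given defibrotide, and no text resolves it. The missing time reference is a second, smaller defect common to both rules on their literal reading; it affects pre-rescue events in rescued BSC subjects.

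The effect is confined to summaries that use relatedness, mainly the BSC column and therefore the descriptive contrast between arms. Its size cannot be computed from the documents, and if no relationship is missing, nothing changes. Primary and secondary efficacy analyses are untouched. A reader might infer from the protocol's SAE presumption that 8.1.1 must be the intended rule. That does not follow: Protocol 6.8.1.5 governs what happens when an initial SAE report lacks causality, and it does not say how tables are built. This is a minor point of consistency, worth correcting because the correction is cheap.

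**What to change.** State one rule in SAP 11.2 and have 8.1.1 cross-refer to it, removing the unconditional rule there and adjusting the sentence that excludes other imputation:

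- A missing relationship is imputed as related if AE onset is on or after the subject's first defibrotide dose, whether prophylaxis or rescue, and as not related otherwise.
- Onset is taken after the date imputation in 8.1.2.1. That section sets a completely missing start date to the first dose date without saying which dose applies to BSC subjects. For a rescued BSC subject, conditioning and the first rescue dose would give opposite relatedness results under the new rule, so the SAP must name the reference date.
- State that the related presumption in Protocol 6.8.1.5 is a reporting default, and say how an SAE carrying it enters the tables: as a recorded value after reconciliation, or as missing and subject to the rule above.

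The cost is a short paragraph in 11.2, a cross-reference in 8.1.1, a clarification in 8.1.2.1 and one programming condition. No new data are needed. SAP Section 3 requires decisions on the final analysis before database freeze, so this should be settled by then.
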